11.3. List of Figures

- Figure 14.2-1.1: Plot of Mean (\pm SD) NRS Scores over Time with Imputation – Efficacy Analysis Set
- Figure 14.2-1.2: Plot of Mean (\pm SD) NRS Scores over Time without Imputation – Efficacy Analysis Set
- Figure 14.2-1.3: Plot of Individual Subject NRS Scores Over Time – Efficacy Analysis Set
- Figure 14.2-2: Bar Chart of Percentage of Pain-Free Subjects – Efficacy Analysis Set
- Figure 14.2-3: Bar Chart of Percentage of Opioid-Free Subjects – Efficacy Analysis Set
- Figure 14.2-4: Plot of Time to First Rescue Medication Use – Efficacy Analysis Set
- Figure 14.2-5: Bar Chart of Subject Satisfaction with Postsurgical Pain Control – Efficacy Analysis Set

12. MULTIPLE IMPUTATION EXAMPLE PROGRAM CODE

** Note: INPUT_DATA is the dataset that contains the NRS data with the wWOOF imputation performed for the rescue pain scores **;

** Step 1 use Markov-Chain Monte-Carlo (MCMC) method to create a monotonic missing pattern **;

** Note the value for the random seed should be fixed so that the results are reproducible **;

PROC MI DATA=INPUT_DATA SEED=M NIMPUTE=1000 OUT=OUTPUT_STEP1;

 BY TREATMENT;

 MCMC IMPUTE=MONOTONE NBITER=2000 NITER=1000;

 VAR TIME_POINT_LIST;

RUN;

** Step 2 – use regression on output dataset from Step 1 to impute missing values **;

** T_i is the variable containing the pain score from time i **;

PROC MI DATA=OUTPUT_STEP1 OUT=OUTPUT_STEP2;

 BY _IMPUTATION_;

 CLASS TREATMENT;

 MONOTONE REG(T_1 = TREATMENT / DETAILS);

 MONOTONE REG(T_2 = TREATMENT T_1 / DETAILS);

...

 MONOTONE REG($T_{(n-1)}$ = TREATMENT $T_1 T_2 T_3 \dots T_{(n-2)}$ / DETAILS);

 MONOTONE REG(T_n = TREATMENT $T_1 T_2 T_3 \dots T_{(n-1)}$ / DETAILS);

 VAR TREATMENT $T_1 T_2 T_3 \dots T_n$

RUN;

** Dataset OUTPUT_STEP2 is as an ADaM dataset, include in DEFINE.XML and transfers **;

** Step 3 derive endpoint using appropriate techniques by variable _imputation_ **;

** Endpoints are: AUC(0.25-48), AUC(0.25-24), AUC(0.25-72), SPI(0.25-24), SPI(0.25-48), **;

** SPI(0.25-72) and integrated rank assessment at 24, 48 and 72 hours **;

** Step 4 get summary statistics **;

** Summary step 4a get the mean of all imputation endpoint values for each subject **;

PROC SUMMARY DATA=OUTPUT_STEP2;

 BY TREATMENT USUBJID;

 VAR ENDPOINT_VARIABLE;

 OUTPUT OUT=SUMMARYSTATSA MEAN=ENDPOINTMEAN;

RUN;

** Dataset SUMMARYSTATSA is as an ADaM dataset, include in DEFINE.XML and transfers **;

** SUMMARYSTATSA also source for a data listing **;

** Summary step 4b use subject imputation means to derive summary statistics **;

PROC SUMMARY DATA=SUMMARYSTATSA;

 BY TREATMENT;

[figure not shown]
 VAR ENDPOINTMEAN;

 OUTPUT OUT=SUMMARYSTATSB N=N MEAN=MEAN STDDEV=STDDEV MEDIAN=MEDIAN
 MIN=MIN MAX=MAX;

RUN;

```
*** Step 5 analyze imputations **;  
ODS OUTPUT ESTIMATES=MIXEDSTATSA;  
PROC MIXED DATA= OUTPUT_STEP2 METHOD=TYPE3;  
    BY _IMPUTATION_;  
    CLASS TREATMENT SITE;  
    MODEL ENDPOINT_VARIABLE = TREATMENT SITE;  
    ESTIMATE 'EXPAREL - PLACEBO' TREATMENT 1 -1;  
RUN;  
  
ODS OUTPUT PARAMETERESTIMATES=MIXEDSTATSB;  
PROC MIANALYZE DATA= MIXEDSTATSA ALPHA=0.05 THETA0=0;  
    MODELEFFECTS ESTIMATE;  
    STDERR STDERR;  

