7.6.2. Methods of Analysis

7.6.2.1. Primary Efficacy Analysis

The primary efficacy analyses will be conducted for both the primary and secondary efficacy analysis sets. Results from the primary efficacy analysis set will be primary efficacy result; the analyses based on the secondary efficacy analysis set are a sensitivity analysis.

The primary efficacy variable is the AUC of NRS scores from first postsurgery assessment (0.25 hours) through 48 hours [AUC(0.25-48)] using the wWOCF to adjust for rescue medication use and multiple imputation method to account for missing data described in Section 7.1.1.1.1.

Tests for the treatment effect of EXPAREL versus placebo will be based on the following null hypothesis (H_0) and two-sided alternative hypothesis (H_a):

$H_0: \mu_s = \mu_p$ versus $H_a: \mu_s \neq \mu_p$

where μ_s and μ_p are the mean of AUC(0.25-48) for EXPAREL and the mean of AUC(0.25-48) for placebo, respectively. A two-sided test will be performed at 5% level of significance. The treatment effect of EXPAREL will be considered significantly better than that of placebo if the null hypothesis of no difference is rejected and a difference in mean of AUC(0.25-48) in favor of EXPAREL (mean for EXPAREL < mean for placebo) is observed.

For the primary efficacy variable of AUC(0.25-48), EXPAREL will be compared to placebo using analysis of variance (ANOVA) with treatment and site as main effects. Based on the model, the least squares (LS) means, LS mean difference between the two treatment groups, 95% confidence interval (CI) for the LS mean difference between the two treatment groups, and p-value will be reported.

Descriptive statistics of the primary efficacy variable will also be shown by site but no statistical analyses will be performed by site.

In addition, an ANOVA model with main effects of treatment and site and the treatment by site interaction will be reported to assess the interaction on the primary efficacy analysis. Additional analyses may be performed if the interaction effect is significant (p-value <0.05).

Sensitivity Analyses

Mixed Model Repeated Measures

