3. ADDITIONAL SUMMARIES

The effect of surgeon will be determined by replacing the site effect in the efficacy analysis of variance with surgeon and by summarizing data by surgeon within site as appropriate (see Section 2 for additional detail). Table B indicated the tables and figures to be produced to explore the surgeon effect and, if applicable, the corresponding table or figure template with a brief description of changes to the planned output.

Table B: Templates and Titles for Surgeon Tables

| | |
|--|------------|
| Surgeon Effect Notes | Table |
| | 14.1-2.1 |
| | 14.1-2.2.1 |
| | 14.1-2.2.2 |
| | 14.1-2.3 |
| These tables will be amended with additional information. The current data planned remains on the table. | 14.1-2.4 |

| | |
|---|---|
| For site 100 create new pages in the table for each surgeon at site 100. The site 100 page will remain as is unchanged. | 14.1-3.1 |
| | 14.1-3.2.1 |
| | 14.1-3.2.2 |
| | 14.1-3.3 |
| Replace site effect in ANOVA with surgeon | 14.2-1.1.1.S: Analysis of AUC of NRS Pain Intensity Scores through 48 hours – Primary Efficacy Analysis Set – Surgeon Effect |
| | 14.2-1.1.6.S: Analysis of AUC of NRS Pain Intensity Scores through 48 hours – Per-protocol Efficacy Analysis Set – Surgeon Effect |
| | 14.2-1.2.1.S: Summary of AUC of NRS Pain Intensity Scores through 48 hours – Primary Efficacy Analysis Set - Analysis of Variance (ANOVA) Model Results – Surgeon Effect |
| | 14.2-1.2.1.S.1: Summary of AUC of NRS Pain Intensity Scores through 48 hours – Per-protocol Efficacy Analysis Set - Analysis of Variance (ANOVA) Model Results – Surgeon Effect |
| | 14.2-2.2.S: Summary of AUC of NRS Pain Intensity Scores through 24 hours – Primary Efficacy Analysis Set - Analysis of Variance (ANOVA) Model Results – Surgeon Effect |
| | 14.2-2.2.1.S: Summary of AUC of NRS Pain Intensity Scores through 24 hours – Per-protocol Efficacy Analysis Set - Analysis of Variance (ANOVA) Model Results – Surgeon Effect |
| | 14.2-3.2.S: Summary of AUC of NRS Pain Intensity Scores through 72 hours – Primary Efficacy Analysis Set - Analysis of Variance (ANOVA) Model Results – Surgeon Effect |
| | 14.2-3.2.1.2: Summary of AUC of NRS Pain Intensity Scores through 72 hours – Per-protocol Efficacy Analysis Set - Analysis of Variance (ANOVA) Model Results – Surgeon Effect |
| Replace site as stratification with surgeon | 14.2-5.1.S: Analysis of Opioid-Free Subjects through 24 hours – Primary Efficacy Analysis Set – Surgeon Effect |

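### The multiple imputation leaves out site, while the ANOVAs run on the imputed data fit site and treatment-by-site: a cheap mismatch to close, with little effect on the primary treatment estimate

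*SAP*

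**What the plan says.** **Analysis model.** SAP 7.6.2.1 sets the primary comparison: "EXPAREL will be compared to placebo using analysis of variance (ANOVA) with treatment and site as main effects". It also states that "an ANOVA model with main effects of treatment and site and the treatment by site interaction will be reported", and then: "Additional analyses may be performed if the interaction effect is significant (p-value <0.05"). The shell of Table 14.2-1.2 prints site and interaction p-values and is titled as multiple imputation results. The matching 24 h and 72 h tables are on the topline list in Section 5.

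**Imputation model.** In Section 12, Step 1 runs MCMC separately by treatment with "VAR TIME_POINT_LIST", so only pain scores enter. Step 2 has "CLASS TREATMENT" and regresses each score on treatment and the earlier scores. Site first appears in Step 5, as "MODEL ENDPOINT_VARIABLE = TREATMENT SITE". The prose in 7.1.1.1.1, steps b and c, names no site covariate. The tipping-point code in 7.6.2.1 repeats the Step 2 regressions without site.

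**Addendum.** Section 3 examines surgeon by "replacing the site effect in the efficacy analysis of variance with surgeon". Its table shells list sites 100 (two surgeons), 200 and 300.

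**The concern.** An imputation model should contain at least the terms of the model later fitted to the imputed data. Here a missing score is drawn as if all sites shared one level and one treatment effect. The imputed value reflects the subject's site only as far as that subject's other scores convey it. Running 1000 imputations removes Monte Carlo noise, but not this.

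Two things follow. The reported site and interaction results can understate real differences between sites. And if dropout is concentrated in particular arm-by-site cells, those cells are filled with values centred on the wrong level, which can shift the treatment difference and create an interaction that is not there.

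**Working it through.** **The plan's own figures.** The documents give no figure for the site or interaction test and no expected missing rate. The sample-size statement (SAP Section 8) serves only as a scale. With 50 per group, a difference of 66 and SD 100 give power 0.905, and 86 with SD 130 gives 0.906 (noncentral t, two-sided 0.05). Both agree with the stated 90%.

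**The models side by side.**

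| Step | Terms used |
|---|---|
| Step 1, MCMC, by treatment | pain scores |
| Step 2, monotone regression | treatment, earlier scores |
| Tipping point | treatment, earlier scores |
| Step 5 and primary ANOVA | treatment, site |
| Second ANOVA | treatment, site, treatment-by-site |

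**Upper bound by arithmetic.** Let D be the true site (or interaction) contrast in AUC and m the fraction of subjects with no score that conveys site. Their imputed AUCs contribute a contrast of 0. The estimate is then (1 − m)·D + m·0 = (1 − m)·D, which is 0.95D, 0.90D and 0.80D at 5%, 10% and 20% missing. If earlier scores convey a share c of the contrast, it is (1 − m(1 − c))·D.

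**Large-sample simulation.** This used the Step 2 regressions on the 10 scheduled scores from 0.25 to 48 h, the trapezoidal AUC and 2:1 allocation. Assumptions not in the documents: two sites, 200,000 subjects per scenario, scores missing completely at random, NRS SD 2.6, within-subject correlation 0.5 to 0.7, and a site shift and an interaction of 1 point each. The Step 1 MCMC was not simulated. Entries are the site and interaction estimates after imputation without site, divided by the complete-data estimates.

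| Missing scores | Site effect | 5% | 10% | 20% |
|---|---|---|---|---|
| all | constant or late | 0.94–0.96 | 0.88–0.90 | 0.79–0.81 |
| from 4 h | constant | 0.99–1.00 | 0.98–0.99 | 0.97–0.99 |
| from 4 h | only from 12 h | 0.94–0.95 | 0.90–0.91 | 0.79–0.80 |
| 24 and 48 h | constant | 1.00 | 0.99–1.00 | 0.99–1.00 |
| 24 and 48 h | only from 12 h | 0.97–0.98 | 0.94–0.95 | 0.88–0.90 |

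The treatment effect stayed at 0.99 to 1.01 of its complete-data value in every scenario. With site and treatment-by-site in the imputation, the site and interaction ratios were 0.98 to 1.02, which is simulation noise.

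The last row can be checked by hand. The trapezoidal weights at 12, 24 and 48 h are 8, 18 and 12, so 30/38 = 0.79 of the late contrast is missing. With no help from the 12 h score the ratios would be 1 − 0.79m = 0.96, 0.92 and 0.84. The simulated values are higher because the 12 h score conveys part of it.

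**Trial-size simulations.** Assumed: 100/60 subjects, three sites, a treatment difference of about 60 AUC units, early scores damped in the first 2 h, 250 to 400 runs, and 10 to 15 imputations.

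- *Even 10% dropout by 2 h, effect doubled at one site.* The interaction contrast falls from 64.5 to 58.3 (6.2/64.5 = 10%). Adding SITE alone does not help (error −6.4). Adding SITE and TREATMENT*SITE restores 64.3. The treatment difference moves by less than 0.3. A separate run of the same kind gave 63.8 falling to 59.1 (4.7/63.8 = 7%), restored only with the interaction term.
- *10% dropout clustered by arm and site.* The treatment difference (59) is off by 1.9 (3%) at a site gap of 2.2 NRS points and by 0.6 (1%) at 1.4. With SITE added the errors are 0.2 and −0.1. A separate run gave 1.5 to 4.4 units (2% to 7% of the planning difference of 66) and a spurious interaction, both removed by adding SITE.

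**Size against sampling error.** Take SD 100 and 100/60 subjects split evenly over three sites. One site's treatment effect has standard error 100·√(1/33.3 + 1/20) = 28.3. Against the mean of the other two sites it is √(28.3² + 28.3²/2) = 34.6. The 6.2-unit shift is 6.2/34.6 = 0.18 standard errors.

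**The case against.** The strongest reply is that this hardly matters here. Subjects stay in the facility for 96 hours (Protocol 13.1), so few scores may be missing. Observed scores and those replaced by the rescue rule keep their site information. When a site effect is constant over time, earlier scores carry most of it and the loss is 0% to 3%. Shrinkage near the full missing fraction needs very early dropout or late-appearing site differences, neither of which the documents predict. The 6.2-unit shift is small beside its standard error, and no change in the p-values that the SAP actually reports was measured. Section 12 is also labelled example code. All of this stands and sets the weight of the point. The label does not remove it, because neither 7.1.1.1.1 nor 7.6.2.1 adds site to the imputation.

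A reader might infer more than the documents support:

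- *That the primary result is compromised.* With even missingness the treatment estimate is essentially unchanged. The shift needs dropout clustered by arm and site together with sizeable site gaps.
- *That the distortion is always toward zero.* That is the usual direction. Opposite early and late site differences, or clustered dropout, can act otherwise.
- *That the interaction test decides what follows.* The SAP says only that further analyses *may* be done.
- *That the surgeon analyses are affected too.* The addendum refers to its Section 2 for detail, which was not fully available for this review. Whether those models use the Section 12 imputation cannot be determined here.

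**Conclusion.** The mismatch is a rule written into the SAP's code and not contradicted by its prose. Its consequence is conditional. The site and interaction estimates lose between nothing and about the missing fraction, on assumed missingness of 5% to 20%. The treatment difference is slightly biased, and a spurious interaction possible, only if dropout is uneven over arm and site. The sizes rest on assumed dropout patterns, site effects and correlations, because the documents give none of these. This is a cheap improvement of low severity. It makes a supportive check and the site-adjusted estimate cleaner, and it does not call the primary conclusion into question.

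**What to change.** In SAP Section 12:

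- **Step 1**, which already runs by treatment: put k − 1 indicators for pooled site (pooling rule in 7.1) at the start of the VAR list, before the scores.
- **Step 2 and the tipping-point call in 7.6.2.1:** add SITE to CLASS, add SITE to VAR before the first score, and add SITE and TREATMENT*SITE as effects in each MONOTONE REG statement. The interaction belongs in the regression effects, not in CLASS.

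State the same in 7.1.1.1.1, steps b and c. If the addendum's surgeon models use this imputation, use surgeon in place of site for them.

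The cost is a few lines of text and code. With three sites, Step 2 gains 2 + 2 = 4 coefficients per regression. If all 12 scheduled scores through 96 h enter, the longest regression goes from 13 coefficients (intercept, treatment, 11 earlier scores) to 17. Judge that against the primary efficacy set, which holds Amendment 2 subjects only (SAP Section 6) and for which Protocol 15.3 aims at no fewer than 50 treated per arm, rather than against the planned total of 175.

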7.1.1. Handling Missing Values

7.1.1.1. Area Under the NRS-Time Curve

7.1.1.1.1. Multiple Imputation Method

Rubin’s (1987)⁴ multiple imputation procedure will be applied to replace each missing value with a set of plausible values that represent the uncertainty about the right value to impute. This multiple imputation method is being implemented per the advice provided in “the prevention and treatment of missing data in clinical trials”⁵ For calculation of area under the curve (AUC) of NRS pain intensity scores, the windowed worst observation carried forward (wWOCF) multiple imputation procedure will be used in the following order:

- Windowed worst observation carried forward (wWOCF) for rescue medications.

For subjects who take a rescue medication, their NRS scores recorded within the window of controlled type of rescue medication (see [Table 2](#)) will be replaced by the ‘worst’ observation. The worst observation will be the highest score from time 0.25 or end of previous rescue window, to

pain score immediately prior to rescue medication for those subjects with pain score prior to each rescue medication (Amendment 2) or, for those subjects with pain scores only prior to first rescue medication use (Amendment 1) in the time interval from time 0.25 to up to the time of rescue medication. The NRS score at rescue will be included in this

calculation. Note that NRS scores in the window that are higher than the worst value prior to rescue medication will not be overwritten.

- b) After the wWOCF imputation, described in Step a, subject data still missing with a non-monotone missing pattern (ie, all pain scores between the last non-missing score and last timepoint) will have missing scores imputed using the Markov-Chain Monte-Carlo (MCMC) method (Schafer 1997)⁶, which will be applied in the multiple imputation procedure for arbitrary missing patterns. This MCMC method will use 1000 imputation datasets with NBITER=2000 and NITER=1000.
- c) The resulting data from Step b will then have the remaining monotone missing patterns, hence a parametric regression method on pain (Rubin 1987) that assumes multivariate normality will be applied for this multiple imputation procedure.
- d) The AUC and SPIS at various time intervals will be derived from the imputed NRS scores resulting from Step c.
- e) The endpoints derived in Step d will be analyzed as described in Section 7.6.2.1 for each imputation.

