- f) Rubin's (1987) synthesizing procedure for the multiple imputed data will be applied to synthesize analysis results for each imputation. SAS PROC MIANALYZE will be used for this procedure. The mean parameter estimates, the asymptotic variance for this mean from the imputed data analysis in Step e will be created based on Rubin and Schenker method (1986)⁷.

For summary statistics based on multiple imputations, the mean value from each imputation will be derived for each subject. These mean values will then be summarized to obtain the summary statistics for reporting.

SAS pseudo-code for multiple imputations is provided in Section 12

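### The pooling of 1000 imputations sets no complete-data degrees of freedom, so as specified the AUC tests use a near-normal reference and are very slightly too favourable

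*SAP*

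**What the plan says.** SAP 7.6.2.1 compares AUC(0.25-48) between arms by ANOVA with treatment and site as main effects, and states: "A two-sided test will be performed at 5% level of significance". SAP 7.6.2.2 analyses AUC(0.25-24) and AUC(0.25-72) in the same manner.

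Missing scores are multiply imputed (SAP 7.1.1.1.1): "This MCMC method will use 1000 imputation datasets with NBITER=2000 and NITER=1000". The code in SAP section 12 agrees: "PROC MI DATA=INPUT_DATA SEED=M NIMPUTE=1000 OUT=OUTPUT_STEP1".

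Step f of 7.1.1.1.1 applies Rubin's 1987 synthesis: "SAS PROC MIANALYZE will be used for this procedure". It describes the variance of the pooled mean as asymptotic and says that it "will be created based on Rubin and Schenker method" of 1986. It names no df.

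Step 5 of section 12 fits "MODEL ENDPOINT_VARIABLE = TREATMENT SITE" within each imputation, then passes only the treatment estimate and its standard error to "PROC MIANALYZE DATA= MIXEDSTATSA ALPHA=0.05 THETA0=0". The options are ALPHA= and THETA0=. The complete-data df option, EDF=, is absent.

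**The concern.** Rubin's large-sample df reflects only the uncertainty from using a finite number of imputations. It grows with that number and takes no account of the number of subjects. With 1000 imputations it is so large that the reference distribution is effectively normal. An ordinary ANOVA on the same subjects would use a t distribution with N minus 4 df.

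At stake are the p-value and confidence interval of the confirmatory analysis. SAP 7.1.2 also opens the secondary sequence only if the primary is significant at 0.05, so a borderline primary result would carry the discrepancy into the sequence. The single-imputation ANOVA in 7.6.2.1 does not pass through this pooling step, so its p-value would differ from the primary one partly because of the reference distribution.

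**Working it through.** **The plan's own figure first.** SAP section 8 claims 90% power with 50 per group for a difference of 66 (SD 100) and of 86 (SD 130), two-sided 0.05 t-test.
- Noncentrality is difference / (SD × √(2/50)): 66/(100 × 0.2) = 3.30, and 86/(130 × 0.2) = 3.31.
- With 98 df, power is 0.904 and 0.906. Both reproduce. That calculation uses a finite-df t reference.

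**Inputs**
- m = 1000 imputations (SAP 7.1.1.1.1 and section 12).
- Model: treatment plus site. Three sites (100, 200, 300) appear in the table templates of the SAP addendum, section 3. Parameters are 1 intercept + 1 treatment + 2 site = 4, so complete-data df = N − 4. Merging small sites under SAP 7.1 would change this by at most 2.
- N of the primary set (Amendment 2 subjects only, SAP section 6): not stated, so assumed:
  - 50/50: the minimum treated under the amendment in protocol 15.3. N = 100, df = 96.
  - 100/50: the SAP section 4 figures, which are in 2:1 ratio. N = 150, df = 146.
  - 50/25 (flagged alternative): back-solved from protocol totals of 100/75 with 1:1 randomization under Amendment 1 and 2:1 under Amendment 2. If a subjects per arm entered under Amendment 1, then 100 − a = 2(75 − a), so a = 50, leaving 50 and 25. N = 75, df = 71.
  - All 175 in the primary set (flagged alternative): df = 171.
- λ, the share of variance due to missing data: not stated; varied from 0 to 0.30.
- Software default: infinite complete-data df when EDF= is absent (an assumption; the documents do not say).

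**Reference df as coded.** Rubin's df = (m − 1)/λ².
- λ = 0.05: 999/0.0025 = 399,600
- λ = 0.10: 999/0.01 = 99,900
- λ = 0.30: 999/0.09 = 11,100

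The two-sided 5% critical value is 1.960 in each case.

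**Actual level with negligible missing data.** Level = 2 × P(T_df > 1.960). Shortfall in interval width = 1 − 1.960/t(0.975, df).

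| Assumed arms | df | Correct critical value | Actual level | Interval too narrow by |
|---|---|---|---|---|
| 50/50 | 96 | 1.985 | 5.29% | 1.3% |
| 100/50 | 146 | 1.976 | 5.19% | 0.8% |
| 50/25 (flagged) | 71 | 1.994 | 5.39% | 1.7% |
| All 175 (flagged) | 171 | 1.974 | 5.16% | 0.7% |

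**Simulation.** 200,000 null ANOVAs per case, normal errors, three sites: 5.36% (N = 75) and 5.24% (N = 150) against 1.960; 4.97% and 5.06% against the t quantile.

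**Effect of missing data.** The Barnard-Rubin df is 1/(1/df_Rubin + 1/df_obs), with df_obs = (1 − λ)·v(v + 1)/(v + 3) and v = N − 4. At λ = 0.10 it gives about 85 df for v = 96 and 130 for v = 146. The critical values are 1.988 and 1.979, and the levels as coded are 5.33% and 5.21%. More missing data widens the gap slightly.

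**When the decision changes.** Only if the pooled |t| lies between 1.960 and the correct critical value. A pooled t of 1.97 gives p = 0.0488 as coded, against 0.0517 (96 df) or 0.0507 (146 df). At the planned effect of 0.66 SD, the noncentrality is 0.66/√(1/50 + 1/50) = 3.30 for 50/50 and 0.66/√(1/100 + 1/50) = 3.81 for 100/50. The chance of landing in the window is then about 0.4% and 0.1% (about 1.0% for 50/25).

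**The case against.** The strongest reply is that section 12 is labelled as example code and 7.1.1.1.1 calls it pseudo-code. It has placeholders for the seed, the variable lists and the endpoint, so production code could add EDF= without contradicting any sentence in the SAP. That is fair as to status: the documents do not show what was finally run. It does not remove the point. This is the only pooling specification in the plan, the text in Step f points to the same large-sample rule, and the option belongs on the PROC statement, which is shown in full.

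A second reply stands: the near-normal reference depends on a software default that the documents do not give.

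A third also stands in part. Step f's reference to the 1986 method concerns the variance of the pooled estimate, not the reference df. It is consistent with a large-sample rule but does not by itself establish one.

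A reader might infer that the true error rate is 5.4%, from 71 df. The documents do not support that as the main case. It needs a 50/25 split, which conflicts with protocol 15.3's aim of at least 50 treated in both arms under the amendment. Nor are any of these figures exact true error rates. The endpoint is a rescue-adjusted AUC of a bounded 0-10 score, for which the t reference is itself an approximation.

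**Conclusion.** The point holds, and it is minor. Followed as written, the pooling refers the three AUC tests to an effectively normal distribution instead of a t distribution with the ANOVA's residual df. The direction is known: p-values slightly too small and intervals slightly too narrow.

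Over the main range of 96 to 146 df, the 5% test runs at about 5.3% to 5.2%. The flagged alternatives are 5.4% at 71 df and 5.2% at 171 df. This rests on four assumptions: the procedure's infinite-df default, the assumed size of the Amendment 2 set, approximately normal errors, and little missing data.

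It would go too far to conclude that type I error control is materially lost or that a clear result would be in doubt. Outside a window of about 0.016 to 0.025 in |t| (up to 0.034 at 71 df), the decision at 0.05 is the same.

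**What to change.** In the pooling statement of SAP section 12, set EDF= to the residual df of the ANOVA being pooled: N − 4 for treatment plus three sites, or N − 6 for the model that adds the treatment-by-site interaction (2 more parameters). In 7.1.1.1.1 Step f, state that the p-value and interval use the Barnard-Rubin adjusted df. Apply the same rule to AUC(0.25-24), AUC(0.25-72) and the sensitivity analyses pooled in this way. State the planned size of the Amendment 2 set, so that the df can be anticipated.

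The change is one code option and one sentence, with no new data or design change. The statistical cost is a very slightly larger p-value and an interval about 0.8% to 1.3% wider over the main range.
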